## 5.5 Definition of baseline

Baseline will be defined as the last non-missing data point prior to the first administration of IMP.

## 5.6 Rounding principles

Generally, no rounding of data will be done prior to calculating statistics. However, if reported data contains more than 8 significant digits it will be rounded to 8 significant digits in the database.

In statistical output and descriptive summaries, the following principles will be followed:

- Data will be presented as reported in input data in listings.
- 2 significant digits will be used for percentages; p-values and similar statistical output will be presented using 4 decimal points.
- Descriptive summaries of all other numerical data (e.g. mean, SD, median etc.) will be presented with one extra decimal compared to reported input data.

## 5.7 Significance level

All hypothesis testing will be two-sided, using a 5% significance level ( $\alpha=0.05$ ).

## 5.8 Multiple comparisons/multiplicity

Statistical tests of efficacy outcomes will be for explorative purposes and no adjustment for multiple tests will be performed.

## 5.9 Handling of dropouts, missing data and outliers

Outliers will be included in summary tables and listings and will not be handled separately in any analyses. Generally, no imputation of data will be performed. However, in case of a substantial amount of missing data, judged to affect analyses conclusions related to secondary and exploratory endpoints, imputation methods might be considered or alternative analysis approaches, for example analysing mean scores instead of total scores.

In case of missing start and stop times of AEs that cannot be investigated further, missing data will be imputed according to a worst-case scenario. That is, start time will be imputed as the closest time point post first intake of IMP and end time as 23:59, resulting in the longest possible treatment emergent duration of the AE.

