### **16.7 Database lock**

When all data have been entered and discrepancies solved, clean file will be declared, the

database will be locked, the code will be broken and the data will be analyzed.

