## 17 STATISTICAL METHODS AND DETERMINATION OF SAMPLE SIZE

The principal features of the statistical analysis to be performed are described in this section. A more technical and detailed elaboration of the principal features will be presented in a separate Statistical Analysis Plan (SAP), which will be signed and approved prior to database lock. All analyses will be performed by CTC AB.

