### 17.1 General

Continuous data will be presented in terms of evaluable and missing observations, arithmetic mean, standard deviation (SD), median, minimum and maximum value.

Categorical data will be presented as counts and percentages. When applicable, summary data will be presented by treatment, and by assessment time. Individual patient data will be listed by patient number, treatment, and, where applicable, by assessment time.

All descriptive summaries and statistical analyses will be performed using SAS Version 9.4 or later (SAS Institute, Inc., Cary, NC).

Baseline will be defined as the last non-missing data point prior to the first administration of IMP.

The primary objective of this study is to evaluate the safety and tolerability of NLX-112. The secondary objective is to evaluate preliminary efficacy endpoints, hence, statistical tests of efficacy outcomes will be for descriptive purposes and no adjustment for multiple tests will be performed.

No imputation of missing data will be performed.

All data will be listed by treatment and patient.

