## 6 CHANGES FROM THE CLINICAL STUDY PROTOCOL

Changes to the planned analyses and the timing of these are summarised in Table 2.

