### 9.2 Analysis of secondary endpoints

#### 9.2.1 *Statistical inferential analysis of efficacy endpoints*

Absolute change from baseline in efficacy endpoints (secondary and exploratory endpoints) will generally be analysed using a linear mixed model with treatment, visit and the interaction

treatment\*visit as fixed categorical effects and subject within treatment as a random effect. The baseline value of the dependent variable will be included in the model as a continuous covariate, to account for possible differences in change from baseline outcomes due the starting baseline level. Visit will be modelled as a repeated effect. Kenward-Roger's approximation for degrees of freedom will be used.

Providing a significant type III F-test for the interaction effect treatment\*visit, differences between least square estimates of NLX-112 and placebo for the same visit (i.e. from the interaction term treatment\*visit, where visit is the same for both NLX-112 and placebo) will be estimated and the corresponding p-value will be presented in tables. In addition, differences between least square estimates of each post-baseline visit and baseline for NLX -112 and placebo respectively (i.e. from the interaction term treatment\*visit, where treatment is the same for the post-baseline and the baseline visit) will be estimated and the corresponding p-value will be presented in tables.

The model proposed above will be used for FAS and is valid, as long as the underlying data is missing at random (MAR). As a sensitivity analysis, the model will also be run for PPS, serving as a validity check for the main FAS analysis. The sensitivity analysis will be a complete case analysis, i.e., only patients with no missing data for the dependent variable will be used.

Model diagnostics, for example Shapiro-Wilk's test for a normally distributed residual term and Leven's test for the homoscedasticity assumption of the residual term as well as Q-Q plots and plotting residuals vs. predicted values, will be performed. If model assumptions are deemed to be violated, an attempt will be made to transform the dependent variable in order to fulfil model diagnostics.

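### Protocol 17.1 rules out imputation, but SAP 5.9 allows imputation or a change of score on a judgement that need not be made blind, and Table 2 does not list the change

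*SAP*

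**What the plan says.** Protocol 17.1 (General): "No imputation of missing data will be performed". No exception is given.

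SAP 5.9 starts from nearly the same place: "Generally, no imputation of data will be performed". It then makes an exception: "in case of a substantial amount of missing data, judged to affect analyses conclusions related to secondary and exploratory endpoints, imputation methods might be considered". The other route it offers is "alternative analysis approaches, for example analysing mean scores instead of total scores".

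SAP 5.9 gives no threshold for a substantial amount, no imputation method, no decision-maker and no date for the decision.

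Four other passages bear on this:

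- SAP 6: "Changes to the planned analyses and the timing of these are summarised in Table 2". Table 2 has four rows: the dropped safety set, the chi-square test replaced by a mixed model, the Wilcoxon tests replaced by mixed models, and the 4×24-hour window for diary and wearable data. None concerns imputation or a change of score.
- Protocol 17 says of the SAP: "which will be signed and approved prior to database lock".
- Protocol 16.7 gives the order of events after cleaning: "database will be locked, the code will be broken and the data will be analyzed".
- SAP 9.2.1 says of the main efficacy model: "The model proposed above will be used for FAS and is valid, as long as the underlying data is missing at random (MAR").

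**The concern.** The two documents give different missing-data rules for the same secondary and exploratory endpoints, and the section meant to record such changes is silent.

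The form of the trigger matters more. It refers to the conclusions of the analyses. Under protocol 16.7 the data are analysed after the code is broken, so conclusions in the ordinary sense exist only after unblinding. Approving the SAP before lock fixes the permission in 5.9. It does not fix the choice later made under that permission. Nor does 5.9 say that the planned analysis must still be shown if another takes its place, so a reader of the study report might not see that a substitution had occurred.

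The trial is small (24 patients, about 16 and 8), and SAP 5.1 rests any inference of superiority on these tests at the two-sided 5% level. Protocol 8.3 intends the data to support the design of further studies. If the analysis could be picked after its result was known, the nominal 5% for the affected comparison would no longer describe the procedure.

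**Working it through.** **Text comparison**

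| Question | Protocol | SAP |
|---|---|---|
| Is imputation allowed? | No (17.1) | Generally no, but may be considered (5.9) |
| What triggers it? | Not applicable | A substantial amount of missing data, judged to affect conclusions (5.9) |
| Which method? | Not applicable | Not stated |
| Blind, or before lock? | SAP approved before lock (17); analysis after the code break (16.7) | Not stated for the 5.9 decision |
| Does the planned analysis stay the reported one? | Not applicable | Not stated |
| Listed as a change? | Not applicable | Not in Table 2 |

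The omission stands out because the SAP is specific elsewhere. Protocol violations are classified before lock (5.3), diary and wearable data need at least 8 hours (9.2.3, 9.2.6), the Box-Cox grid is given (9.2.1), and the worst-case rule for adverse-event times is fully defined in 5.9 itself.

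**Is the clause needed?** For missing visits, no: the 9.2.1 model uses the available visits and is stated to be valid under MAR. For missing items there is a real gap, since the SAP does not say how a total is formed when an item is missing. The UDysRS has 104 / 4 = 26 items (protocol 11.3.2). With all K items present, mean = total / K, which is only a rescaling and leaves the p-value unchanged. When items are missing, K × (mean of the answered items) fills each gap with the patient's own item average, which is an implicit imputation.

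**Size.** The documents give no figure to reproduce: there is no sample-size calculation and no assumed dropout rate. All missingness rates, correlations and imputation methods below are assumptions.

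*Independent-test illustration:* 1 − 0.95² = 0.0975 for two analyses and 1 − 0.95³ = 0.1426 for three. Analyses of the same data are strongly correlated, so the real figures are lower.

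*Null simulation 1.* 16:8 patients, 26 items scored 0-4, baseline-to-visit latent correlation 0.5, baseline-adjusted ANCOVA at one visit, two-sided 0.05, 6,000 runs per row (5,516 to 5,999 usable).

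| Visits missing | Patients with items missing | Total, no imputation | Mean score | Baseline carried forward | Any of the three |
|---|---|---|---|---|---|
| 5% | 10% | 0.0549 | 0.0534 | 0.0530 | 0.0739 |
| 10% | 20% | 0.0525 | 0.0518 | 0.0463 | 0.0821 |
| 20% | 20% | 0.0424 | 0.0455 | 0.0435 | 0.0744 |
| 20% | 30% | 0.0502 | 0.0526 | 0.0508 | 0.0903 |
| 12.5% | 0% | 0.0533 | 0.0533 | 0.0563 | 0.0658 |

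Each fixed analysis lies between 0.042 and 0.056. The best of three lies between 0.066 and 0.090. In the last row no items are missing, and total and mean score agree exactly, as the algebra requires.

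*Null simulation 2.* The candidates are available-case, last observation carried forward (LOCF) and baseline carried forward (BOCF). Without any preceding test, about 5% rises to 6.6-8.9% for the best of the three.

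*With the 9.2.1 condition.* SAP 9.2.1 estimates same-visit treatment differences only after a significant treatment-by-visit interaction. This was approximated by a t-test on Day 42 minus Day 28, with correlations 0.6/0.6/0.7 and 10-30% of Day 42 visits missing. The available-case rate without the condition is 4.6-5.1%, and 6.0-7.8% for the better of available-case and LOCF. With the condition these become 0.8-1.0% and 1.0-1.4%.

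**The case against.** Several points on the other side are sound.

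- **The default survives.** SAP 5.9 still says that data will generally not be imputed, and 9.2.1 still names the mixed model on the full analysis set. A reader might infer that the SAP has replaced the protocol's rule for every efficacy endpoint. It has added a vague contingency to it.
- **The trigger need not be unblinded.** The amount of missing data can be counted blind, and the effect on conclusions could be forecast from it. The missing-data decision recorded in Table 2, the 4×24-hour window, is dated before database lock. A reader might infer that the judgement can only be made by looking at treatment results; the documents do not support that. They also do not rule it out, and that part of the concern stands.
- **A mean score is not a new endpoint when items are complete.** It differs from the total only where items are missing.
- **The 7-9% does not describe the main path.** It applies to a single comparison with no preceding test, and it assumes that the option is exercised in every data set, including those with little missing. LOCF and BOCF are not named in the SAP. With the interaction condition the rate is near 1%. The Wilcoxon back-up has no such condition, so the protection does not extend to it.
- **The stakes are limited.** The primary objective is safety. SAP 5.1 and 5.8 call the efficacy findings indicative and the tests explorative, without multiplicity adjustment.

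The exploratory label does not answer the point fully. Unadjusted tests are visible because all are shown, whereas one analysis put in place of another may not be.

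**Conclusion.** The concern holds in a limited form. The protocol and SAP conflict on imputation, Table 2 omits the change, and the wording of 5.9 permits a result-dependent choice of analysis for secondary and exploratory endpoints because it neither ties the decision to a blinded stage nor protects the planned analysis as the reported one. Nothing elsewhere in either document closes that gap.

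The size is modest: roughly 7-9% instead of 5% for one comparison not conditional on another test, and near 1% on the interaction-conditional mixed-model path. These figures depend on assumed missingness, assumed correlations and assumed candidate methods. The figure for the conditional path also rests on a t-test approximation and did not include mean scores.

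A reader might infer that results were, or were meant to be, selected this way. The documents show only what the text allows. The change is worth making because it is cheap and because SAP 5.1 bases any superiority inference on these tests.

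**What to change.** In SAP 5.9:

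1. Delete the trigger that refers to the conclusions of the analyses.
2. State that the no-imputation analysis of 9.2.1, including its pre-specified transformation and Wilcoxon back-up, is always the reported analysis, applied to each endpoint as defined in its own section. This wording keeps the back-up plan and also fits ON time, CGI-C and the wearable measure, which have no total score.
3. Set one item-level rule for deriving scale totals when items are missing, fixed at blinded review before database lock.
4. Allow any imputed or alternative-score analysis only as a sensitivity analysis, chosen and documented before lock and shown beside the planned one.

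In SAP Table 2, add a row for any departure from protocol 17.1 that is kept.

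The cost is a few sentences and one table row, with no change to data collection. The downside is that the team gives up the freedom to change method after unblinding.

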## 6 CHANGES FROM THE CLINICAL STUDY PROTOCOL

Changes to the planned analyses and the timing of these are summarised in Table 2.

**Table 2 Changes in the planned statistical analyses**

Change category	Timing of change	Description of change	Reason for change	Responsible for change
Change in the SAP compared to the CSP	Prior to DBL	The safety analysis set has been omitted.	Safety evaluations based on FAS is considered sufficient.	[name]
Change in the SAP compared to the CSP	Prior to DBL	The Chi2 test for the ON Time Without Troublesome Dyskinesia analysis has been replaced with a linear mixed model approach.	The CSP prescribes that a chi-square test be performed for ON Time Without Troublesome Dyskinesia data for the whole study period. As there are multiple measurements per patient and visit, it is not clear how this can be implemented. Hence a shift to a mixed model approach has been adopted.	[name]
Change in the SAP compared to the CSP	Prior to DBL	Wilcoxon signed rank tests have been replaced with linear mixed modeling with a non-parametric back-up plan should model assumptions fail.	In order to use all available data in the same model, potentially resulting in higher power in the analyses, a mixed model approach has been adopted instead.	[name]
Change in the SAP compared to the CSP	Prior to DBL	The Kinesia 360 wearable dyskinesia assessment system and PD home dyskinesia diary data for up to 4*24 hours prior to Visit 6 and 7 is included in the analyses.	The CSP prescribes data from only up to 2*24 hours to be used in Kinesia 360 wearable device and home diary analyses. However, using the cut-off point of 4*24 hours prior to Visit 6 and 7 respectively was deemed medically acceptable, whereas at the same time minimizing the amount of missing data in the corresponding analyses.	[name]

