#### 4.3 Randomization and number of subjects

On Day 1, patients were randomized to receive either NLX-112 or placebo with the ratio 2:1 for active treatment to placebo. This will give approximately 16 patients who received NLX-112 and 8 patients who received placebo in the study. In addition, approximately the same ratio was intended to be attained within each site. The study used competitive enrolment between 5 sites.

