### 5.2 Sample size calculation

No formal sample size calculation has been performed. The sample size of 24 patients is considered sufficient to evaluate the primary objective and to allow for a preliminary efficacy evaluation.

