Produce the table above for PPS as well, providing there is any de facto difference between the analysis sets. If the LMM is performed using transformed data, insert a footnote about this as well. If the LMM approach is dropped in favour of non-parametric tests, update the table and footnotes accordingly.

**Table UD 2 UdysRS total score for Part III and IV – Most severe assessment session and highest questionnaire item score (Full analysis set)**

Use the same format as for Table UD 1. Produce the table above for PPS as well, providing there is any de facto difference between the analysis sets. If the LMM is performed using transformed data, insert a footnote about this as well. If the LMM approach is dropped in favour of non-parametric tests, update the table and footnotes accordingly.

**Table UD 3 UdysRS total score for Part III and IV – Average of assessment sessions and highest questionnaire item score (Full analysis set)**

Use the same format as for Table UD 1, but update the explanatory footnote to reflect the content of the table. Produce the table above for PPS as well, providing there is any de facto difference between the analysis sets. If the LMM is performed using transformed data, insert a footnote about this as well. If the LMM approach is dropped in favour of non-parametric tests, update the table and footnotes accordingly.

**Table UD 4 UdysRS total score for Part III– Most severe assessment session and sum of questionnaire item scores (Full analysis set)**

Use the same format as for Table UD 1, but update the explanatory footnote to reflect the content of the table. Produce the table above for PPS as well, providing there is any de facto difference between the analysis sets. If the LMM is performed using transformed data, insert a footnote about this as well. If the LMM approach is dropped in favour of non-parametric tests, update the table and footnotes accordingly.

**Table UD 5 UdysRS total score for Part III– Average of assessment sessions and sum of questionnaire item scores (Full analysis set)**

Use the same format as for Table UD 1, but update the explanatory footnote to reflect the content of the table. Produce the table above for PPS as well, providing there is any de facto difference between the analysis sets. If the LMM is performed using transformed data, insert a footnote about this as well. If the LMM approach is dropped in favour of non-parametric tests, update the table and footnotes accordingly.

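### For each outcome, the choice between mixed model, Box-Cox model and rank test rests on undefined diagnostics, apparently after code break, and the SAP does not require the dropped result to be shown

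*SAP*

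**What the plan says.** Protocol 17.6 and 17.7 name one test per outcome. The SAP changes this, and Table 2 summarises the change as "Wilcoxon signed rank tests have been replaced with linear mixed modeling with a non-parametric back-up plan should model assumptions fail".

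The working rules are in SAP 9.2.1:

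- **Step 1** is a linear mixed model on absolute change, with treatment, visit, their interaction and baseline. Between-arm contrasts by visit follow only if the interaction F-test is significant.
- **Diagnostics** are Shapiro-Wilk, Levene, Q-Q plots and residual plots. They are offered as examples, with no threshold, no rule for combining them and no named decision-maker.
- **Step 2**: "If model assumptions are deemed to be violated, an attempt will be made to transform the dependent variable in order to fulfil model diagnostics". The Box-Cox grid runs from -3 to 3 in steps of 0.25.
- **Step 3**: if assumptions are again deemed violated, the model is abandoned for that dependent variable. A Wilcoxon rank sum test on relative change takes its place, with no interaction condition.

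On timing, Protocol 16.7 says that, once the data are clean, the "database will be locked, the code will be broken and the data will be analyzed". SAP 4.5 likewise ties disclosure of allocation to clean file and database lock.

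On display, the instruction below Table UD 1, repeated for every other efficacy table in SAP 10.2.3 and 10.2.4, is: "If the LMM approach is dropped in favour of non-parametric tests, update the table and footnotes accordingly". A transformation is disclosed by footnote.

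On weight, "All hypothesis testing will be two-sided, using a 5% significance level" (SAP 5.7), while "Statistical tests of efficacy outcomes will be for explorative purposes and no adjustment for multiple tests will be performed" (SAP 5.8). SAP 5.1 calls significant findings indicative, yet bases any inference of superiority on these tests.

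**The concern.** Three features combine. The trigger for leaving the model is discretionary. The model being diagnosed contains treatment, so fitting it requires the allocation and produces the arm comparison. And the efficacy tables need not show what the abandoned analysis gave. A reader of the clinical study report would learn from a footnote that a switch was made, but could not tell whether the switch changed the conclusion.

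The branches are also not interchangeable. They use different scales (absolute and relative change), and only the model branch must pass the interaction test before a between-arm p-value is due. Moving to the rank test therefore changes how likely a significant between-arm result is to appear at all.

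**Working it through.** **Inputs from the documents.** Two-sided 5% level (SAP 5.7); no multiplicity adjustment (SAP 5.8); about 16 against 8 patients (SAP 4.3: "This will give approximately 16 patients who received NLX-112 and 8 patients who received placebo in the study"); two post-baseline efficacy visits; the Box-Cox grid above. SAP 5.2 states "No formal sample size calculation has been performed", so there is no power or effect size to reproduce. The only figure to check is the 5% level.

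**Number of outcomes.** UDysRS 5, diary 1, UPDRS 2, CGI-C 1, wearable 1, KPPS 8 (7 domains and total), PDQ39 9 (8 dimensions and total), HADS 2, ICIQ-OAB 1, ESS 1. The sum is 31.

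**How often a path decision would arise.** The SAP gives no cut-off, so I assume Shapiro-Wilk and Levene at 5% each. If the two were independent, a valid model would be flagged with probability 1 - 0.95² = 9.75%. Simulation gives 10–12% with normal data, or about 31 × 0.10 = 3.1 to 31 × 0.12 = 3.7 outcomes. With skewed data the model is flagged in 26–71% of trials. The rank test is reached in 6–8% (normal) and 13–46% (skewed). Even with one 5% diagnostic per outcome, the chance of at least one false alarm is 1 - 0.95³¹ = 79.6% under independence.

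**Error at Day 42 with no treatment effect.** The simulation used 4,000 trials per scenario, 16:8, baseline plus two visits and no dropout. It assumed compound symmetry and Satterthwaite degrees of freedom in place of Kenward-Roger. Further assumptions are between-visit correlation 0.5, 0.7 or 0.85, and normal or log-normal scores (log-SD 0.3 or 0.5). Monte Carlo standard error near 5% is √(0.05 × 0.95 / 4000) = 0.34 points.

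| How the reported p-value is chosen | Rate of p < 0.05 |
|---|---|
| Mixed model always, no interaction condition | 4.8–5.6% |
| Box-Cox model always, no interaction condition | 4.9–5.8% |
| Rank sum always (exact attained size 4.48%) | 4.0–4.8% |
| Fixed order, mechanical 5% diagnostics, no interaction condition | 4.8–6.1% |
| Best of three, no interaction condition | 6.6–8.4% |
| Mixed model with the interaction condition | 0.8–1.4% |
| Best of three, interaction condition on both models | 4.4–5.3% |

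A separate single-visit check, with ANCOVA standing in for the model contrast and no Box-Cox step, gave 4.6–4.7% for mechanical switching. It gave 4.9–5.9% when a failed diagnostic was used only if the rank test was more favourable.

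**Asymmetry between branches.** Scenario by scenario, the rank test without the condition is about 3 times (0.044 / 0.014 = 3.1) to 5 times (0.046 / 0.009 = 5.1) as likely to give a significant null result as the model with it.

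**The case against.** The plan is not a free choice among three analyses. The order is fixed, the diagnostics are named, and the Box-Cox grid is specified. Applied mechanically, the sequence stays close to 5%. A reader might infer that the plan inflates error to 7% or 8%. The documents do not support that: such figures need an analyst who keeps the best result even when every diagnostic passes. With the interaction condition enforced as written, even that gives 4.4–5.3% at Day 42.

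A reader might also infer that the person choosing the path will have seen the arm comparison, or that unfavourable results will be hidden. Neither is stated. Unblinded timing follows from the sequence lock, code break, analysis, but no section says who runs the diagnostics or what they see first. Updated footnotes would disclose a switch, and patient-level data are listed.

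Disagreement between the tests under a true effect (13–19% of data sets in a single-visit check at 1 SD) is not an error rate. Two tests at intermediate power will differ, and with normal data most disagreements have the model significant and the rank test not. Part of the disagreement also comes from the rank test's use of unadjusted relative change, not from when the path is chosen.

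Finally, the primary objective is safety and the efficacy tests are exploratory. Leaving the protocol's signed-rank test was itself sound, because a paired test cannot compare independent arms.

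All of this limits the size of the problem. It does not supply the missing cut-offs, describe a blinded step, or require the dropped result to be shown.

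**Conclusion.** The point holds as one of transparency and pre-specification, with a modest effect on error. Per test, expect about 4.6–6.1% if a 5% diagnostic rule is applied mechanically and about 5–6% if failed diagnostics are used selectively. The 6.6–8.4% range is an upper bound that also sets the interaction condition aside. These figures rest on the assumed cut-offs, correlations and score distributions, and on no dropout.

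The clearer consequence is that the branch decides what is reported: a null between-arm result appears as significant in about 1% of trials on the model branch and 4–5% on the rank branch. The explorative label lowers the importance, but SAP 5.1 still rests any inference of superiority on these p-values. I class this as a cheap improvement.

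**What to change.** **Main change.** For every outcome and visit, print two rows in Tables UD 1, CG 1 and KP 1 and the tables that copy them:

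- the baseline-adjusted mixed-model contrast (estimate, confidence interval, p-value), whatever the interaction test shows;
- the rank-based p-value.

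Name the mixed model as the lead result, show any transformed model only as an addition, and delete the instruction to update the table when the model is dropped. Make these changes together: lifting the interaction condition while keeping the discretionary switch would bring the 6.6–8.4% bound into play.

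**If the sequence is kept.** State numeric cut-offs and how they combine. Sign off the path for each outcome before code break, using residuals from the model fitted without treatment. Numeric cut-offs alone would settle much of the concern; making the untransformed model the lead for all 31 variables is partly a matter of preference.

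**Cost.** SAP wording and one or two extra rows per efficacy table. Data collection and sample size are unaffected. The downside is that a model that may fit poorly is shown beside its rank check. Side-by-side reporting remains possible even after the code has been broken.
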